#### 4.4.3. Exploratory Aims

In order to examine the relationship between observed communication from audio-recordings and patient satisfaction, we will evaluate the correlation between the numbers of discussions regarding age-related concerns from audio-recorded visits with patient satisfaction on HCCQ.

We will determine the association of baseline oncology physician and patient decision-making preferences on the likelihood of having a discussion related to geriatric domains. The analysis for PCORI Primary Aim will be used with the above characteristics added as independent variables. The statistical significance and estimated coefficients will be used to identify and interpret potentially important baseline features. Any conclusions will be considered to be hypothesis generating for further research.

We will also measure if the intervention influences the proportion of discussions during which an oncology physician responds appropriately to an older patient or caregiver-initiated discussion on age-related needs and concerns (e.g., oncology physician response/(number of patient and caregiver concerns)).

We will capture survival through the participant's medical record and verification with the primary team. We will follow participants for survival for 12 months after enrollment. We will obtain the date, location of death, and cause of death. If a site becomes aware that a study participant is deceased, they should complete the Withdrawal form which is available on the URCC NCORP website. Otherwise sites will be contacted approximately 1 year after each participant was enrolled to assess survival and asked to complete this form. We will determine the effect of the intervention on 12-month survival using log rank tests and survival plots.

We will also verify information with Medicare claims data if the participant provided permission to do this through initial consent. In order to assess health care utilization (e.g., adverse events such as hospitalizations) for future work on examining cost-effectiveness of the intervention, permission to obtain Medicare claims in the future was asked on the consent form. Claims will not be obtained for any individual patient until the patient has completed study procedures. All consent and research procedures for obtaining Medicare claims will be followed:

<http://www.cms.gov/Research-Statistics-Data-and-Systems/Computer-Data-and-Systems/Privacy/Researchers.html>

Permission to obtain claims is voluntary and patients are able to decline this procedure at the time of consent. Declining consent for obtaining claims from Medicare for future research to examine cost-effectiveness, quality of care, and health care utilization did not preclude patients from participating in this study.

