2.2. Secondary Aims

2.2.1. Secondary Aim 1 (primary aim as specified by PCORI): To determine if providing GA summary plus GA-driven recommendations to patients, their caregivers, and oncology physicians increases **discussions** about age-related issues during clinic consultation.

Hypothesis: A higher proportion of age-related issues will be discussed and addressed in the intervention group.

The outcome measure for this aim is the number of age-related discussions related to the different aspects of geriatric assessment that occur in the consultation clinic visit between the patient, oncology physician, and caregiver. The clinic visit will be audio-recorded. This outcome was accepted as the primary aim by PCORI.

2.2.2. Secondary Aim 2: To determine whether initially providing patients, their caregivers, and oncology physicians with GA summary plus GA-driven recommendations prior to their treatment influences **quality of life** of older patients receiving treatment and their caregivers.

2.2.3. Secondary Aim 3: To determine whether providing patients, their caregivers, and oncology physicians with GA summary plus GA-driven recommendations influences **caregiver satisfaction with communication** about age-related issues.

2.3. Exploratory Aims:

Exploratory aims will evaluate (1) whether the number of discussions about age-related issues during the clinic visit correlates with patient satisfaction, (2) whether the intervention increases the proportion of age-related concerns that are acknowledged and addressed, and (3) if communication about age-related issues influences how patients, caregivers, and oncology physicians make decisions for cancer treatment. An additional exploratory aim will examine the impact of the intervention on survival.

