10. INTERVENTION OVERVIEW FOR PHYSICIANS

Practice sites will be notified if they are in the intervention arm by URCC Research Base staff. Prior to the intervention, oncology physicians will receive training on how to best utilize GA information in clinical practice for older adults with cancer. The training session provides a brief overview of the intervention information and can be completed through a web conference, telephone call, or as a paper “sign-off” documenting review of the materials. The training materials were developed with resources from Drs. [name]’s and [name]’s geriatric oncology lectures.

The CRAs and/or research nurses at sites randomized to the intervention arm will be trained to utilize the [mycarg.org website](http://mycarg.org) to derive a summary of GA scores and a list of targeted GA-driven recommendations.

This information will be printed by the site CRAs for the oncology physician who will “sign off” that he/she has received and reviewed the information. Study or clinical staff can assist the physician in checking which recommendations were considered and facilitating implementation of GA-driven recommendations. Two copies of the summary and checklists should be made: one should be provided to the patient/caregiver and one should be retained in the study chart. Patients and caregivers should be provided with a copy of the GA summary and GA-driven recommendation forms prior to the audio-recorded visit. The original forms should be submitted to the URCC Research Base.

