In order to examine the relationship between observed communication from audio-recordings and patient satisfaction, we will evaluate the correlation between the numbers of discussions regarding age-related concerns from audio-recorded visits with patient satisfaction on HCCQ-age (modified to evaluate for satisfaction for communication about age-related issues). We will determine the association of baseline oncology physician and patient decision-making preferences on the likelihood of having a discussion related to geriatric domains. The analysis for PCORI Primary Aim (secondary aim 1) will be used with the above characteristics added as independent variables. The statistical significance and estimated coefficients will be used to identify and interpret potentially important baseline features. Any conclusions will be considered to be hypothesis generating for further research.

We will also measure the intervention increases the proportion of age-related issues that are acknowledged and addressed (e.g., oncology physician response/(number of patient and caregiver concerns). We will examine if the intervention improves physician confidence with managing age-related conditions as well as physician comfort with communication about age-related issues (using data from physician baseline and follow up forms)

We will capture survival through the participant's medical record and verification with the primary team. We will follow participants for survival for 12 months after enrollment. We will obtain the date, location of death, and cause of death. If a site becomes aware that a study participant is deceased, they should complete the withdrawal form if the survival status form is not yet available on the URCC NCORP website. Otherwise sites will be contacted approximately 1 year after each participant was enrolled to assess survival and asked to complete this form. We will determine the effect of the intervention on 12-month survival using log rank tests and survival plots.

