#### 2.3.1 Primary Aim (as specified by NCI)

To determine if providing geriatric assessment (GA) summary plus GA-driven recommendations to patients, their caregivers and oncology **physicians improves patient satisfaction with communication with the oncology physician** regarding age-related concerns.

*Primary hypothesis:* Patient satisfaction with communication with the oncology physician about age-related issues will be significantly higher in the intervention group compared to the control group.

The NCI primary outcome, patient satisfaction regarding communication about age-related issues as measured by a modified Health Care Climate Questionnaire (HCCQ-age), will be obtained by the Telephone Team, via a phone call administered by trained personnel blinded to group assignment within 1 to 7 days of the baseline audio-recorded clinic consultation. The HCCQ-age will be mailed (with a return envelope) if a telephone call is not feasible. If the responses to the survey are not able to be obtained before the 4-6 week assessment, the HCCQ-age at 4-6 weeks will be utilized.

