### **2.3.2 Secondary Aim 1 (Primary Aim as specified by PCORI)**

To determine if providing GA summary plus GA-driven recommendations to patient, their caregivers, and oncology physicians increases discussions about age-related issues during clinic consultation.

*Primary hypothesis:* A higher number of age-related issues will be discussed and addressed in the intervention group.

The outcome measure for this aim is the number of age-related discussions that occur in the consultation clinic visit between the patient, oncology physician, and caregiver. The clinic visit will be audio-recorded.

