#### 3.4.1 Sample Size for NIH-specified Primary Aim

We will utilize the modified HCCQ to address patient satisfaction with communication regarding age-related issues (HCCQ-age). Based on an analysis of the VOICE study, the standard deviation estimate of HCCQ was 2.1. The Intraclass Correlation (ICC) was 0.14 with a 95% confidence interval from 0.01 to 0.51. Because of the large amount of uncertainty in the ICC, we calculated power curves for ICC={0.01, 0.14, 0.51}, with ICC=0.51 being the most conservative. This design (8 sites per arm and 31 subjects per site) has 80% power at the 0.05 significance level to detect a change in HCCQ of 0.6, 1.3 and 2.3 for ICC={0.01, 0.14, 0.51}, respectively. Since the best estimate of the ICC is 0.14, the expected detectable difference is 1.3. This corresponds to an effect size of 0.62. The range of the HCCQ-age scores is 7 (worst possible) to 35 (best possible). Analyses will be based on the HCCQ variables being a continuous variable. We will use a generalized mixed model to confirm robustness. The sample size figure below shows the power for a range of detectable differences (D) for ICC=0.01, 0.14 and 0.51. Small changes in satisfaction scores have been interpreted in other studies to be meaningful given a focus on achievement of high satisfaction scores and the link with reimbursement. In addition to evaluating HCCQ-age using the total score as a continuous variable, we will compare the results for each question as a dichotomous variable (5 vs <5). If the distribution is skewed, we will consider treating HCCQ-age as an ordinal variable in analyses.

Accounting for a small dropout rate of 5% (based on our observational cohort data), the targeted accrual will be **528 patient subjects total**. The dropout rate reflects patients who sign consent but withdraw prior to the audio-recorded baseline visit and capture of HCCQ-age (which will occur within 7 days of baseline visit). To date out of 479 evaluable patients we currently have received 407 baseline HCCQ-ages; 4-6 week HCCQ-ages will be substituted per protocol for 33 patients; there are 19 patients that have no baseline HCCQ-age because they either died or withdrew before the 4-6 week visit, this brings us to a current total of 440 baseline HCCQs to be used in the per protocol analysis.

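### Exploratory Aim 1 plans a discussions–satisfaction correlation with no arm or site term, so it mixes any within-arm association with the intervention's effect on both variables (minor).

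*SAP*

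**What the plan says.** The aim, in Protocol 2.3 and in the same terms in SAP 2.3.4, is to evaluate "whether the number of discussions about age-related issues during the clinic visit correlates with patient satisfaction".

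The analysis is one sentence in each document. SAP 4.4.3: "we will evaluate the correlation between the numbers of discussions regarding age-related concerns from audio-recorded visits with patient satisfaction on HCCQ". Protocol 15.4.3: "we will evaluate the correlation between the numbers of discussions regarding age-related concerns from audio-recorded visits with patient satisfaction on HCCQ-age". Neither names a coefficient, a test, an arm term, stratification, restriction to one arm, or any allowance for site. They also differ on the outcome: HCCQ in the SAP, HCCQ-age in the protocol. The SAP's table of patient measures (3.7.1) lists these as separate measures.

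The two variables are the trial's two main outcomes, and the intervention is expected to raise each:

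- Satisfaction (SAP 2.3.1): "Patient satisfaction with communication with the oncology physician about age-related issues will be significantly higher in the intervention group compared to the control group".
- Discussions (SAP 2.3.2): "A higher number of age-related issues will be discussed and addressed in the intervention group".

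Protocol section 10 adds a route from intervention to patient that does not pass through what is said in the consultation: "Patients and caregivers should be provided with a copy of the GA summary and GA-driven recommendation forms prior to the audio-recorded visit".

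**The concern.** If arm raises both variables, arm is a common cause of them. Intervention patients then sit higher on both scales and control patients lower on both, and that alone tilts a pooled scatter upwards. A positive correlation could mean that patients who had more discussions were more satisfied. It could equally mean only that the intervention changed both things separately. The planned statistic cannot tell these apart.

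A second, smaller matter is that a plain correlation treats patients of one site as independent, although the plan's own ICCs are 0.14 for HCCQ and 0.122 for discussions.

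What is at stake is how one exploratory result is read. A reader would be inclined to take it as evidence that talking about age-related issues goes with satisfaction, when part of it may restate the two arm comparisons.

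**Working it through.** **Inputs.** From SAP 3.4.1 and 3.4.2 (same figures in Protocol 15.2 and 15.3):

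- HCCQ: SD 2.1, ICC 0.14, detectable difference 1.3, effect size 0.62.
- Discussions: SD 0.78, ICC 0.122, detectable difference 0.456, effect size 0.59.
- Design: "8 sites per arm and 31 subjects per site) has 80% power at the 0.05 significance level", that is 16 × 31 = 496 patients.
- 440 HCCQ values in hand at the SAP date, and 68 practice sites in February 2017.

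Assumptions: two-sided 5% test; 1:1 allocation; for 68 sites, equal sizes of 7 with 34 sites per arm (476 patients); site effects on the two variables independent of each other.

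**Step 1: reproduce the plan's effects.** With k sites per arm and m patients per site, SE = SD × √(2(1 + (m − 1)ICC)/(km)). For k = 8 and m = 31:

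- HCCQ: 2.1 × √(2 × 5.20/248) = 0.430. The noncentral t with 14 df gives a detectable difference of 1.296 (stated 1.3).
- Discussions: 0.78 × √(2 × 4.66/248) = 0.151, giving 0.456 (stated 0.456).

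In SD units these are 1.3/2.1 = 0.619 and 0.456/0.78 = 0.585.

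**Step 2: correlation induced by arm alone.** With no association within either arm and arm effects d1 and d2 in SD units,

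r = (d1·d2/4) / √((1 + d1²/4)(1 + d2²/4)).

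At the plan's stated effects: 0.0905 / √(1.0958 × 1.0854) = 0.083.

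**Step 3: the same at other effects.**

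| Arm effects (HCCQ, discussions; SD) | Source | Induced r |
|---|---|---|
| 0.286, 0.301 | plan's low-ICC differences (0.6/2.1, 0.235/0.78) | 0.021 |
| 0.354, 0.343 | detectable with 68 × 7 (assumed layout) | 0.029 |
| 0.619, 0.585 | plan's best-estimate ICCs, 16 × 31 | 0.083 |
| 1.095, 1.233 | plan's high-ICC differences (2.3/2.1, 0.962/0.78) | 0.252 |
| either one zero | arm moves one variable only | 0 |

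The 68 × 7 row uses the Step 1 formula in SD units with k = 34 and m = 7. The SEs are √(2 × 1.84/238) = 0.124 and √(2 × 1.732/238) = 0.121, and the noncentral t with 66 df gives 0.354 and 0.343.

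**Step 4: how often a naive 5% test would call it significant.** By Fisher z at n = 440, ignoring clustering:

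- r = 0.083: z = 0.083 × √437 = 1.74, so 41%.
- r = 0.029: z = 0.62, so about 9%.

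Simulations (8,000 runs) with the stated ICCs and zero within-arm association give:

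- Plan's stated effects: 47% for 16 × 31 and about 45% for 68 × 7. The mean arm-adjusted correlation is 0.000 in both.
- Effects detectable with 68 × 7: about 11–12%.

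**Step 5: clustering alone.** With no arm effect on either variable, the naive test rejects in about 6% of runs for 68 × 7 and about 11% for 16 × 31. At the current number of sites this adds little.

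**The case against.** The strongest reply is that pooling is not written down. The text names no method at all, so the fault is under-specification rather than a chosen pooled analysis. SAP 4.1 makes mixed models with arm fixed and site random the general method, and requires all regressions to control for site. A correlation fitted as a regression would fall under that rule. This stands in part. Pooling is inferred, but it is the natural reading: the neighbouring uptake analysis (SAP 4.4.1) says when it uses only the intervention arm, and this one does not. The SAP 4.1 rule speaks of regressions and does not clearly reach a correlation coefficient.

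Second, the aim is descriptive. It asks whether the two correlate and attaches no causal or mediation claim. That is correct, and it is a main reason for the low severity. The sentence labelling conclusions as hypothesis generating follows the decision-making-preference analysis; even if it covers this one, a label does not remove a predictable component from the estimate.

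A reader might infer that a successful intervention all but guarantees a positive finding here. The figures do not support that. At the plan's stated effects the induced r is 0.083, under 1% of variance, and is significant in fewer than half of trials. Those effects also belong to the 16-site design; at the smaller effects detectable with 68 equal sites, rejection is about 9–12%. The component also requires satisfaction to rise by a route other than discussions. Protocol section 10 makes that possible but does not show that it happens.

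**Conclusion.** The point holds as a minor one. Read naturally, the planned correlation combines any within-arm association with a part produced by arm. That part ranges from negligible to moderate: r about 0.02 to 0.25 across the plan's own effect sizes, 0.08 at its best-estimate effects, about 0.03 at the effects detectable with the assumed 68-site layout, and zero if arm moves only one variable. All these figures take the extreme case of no within-arm association, and the 68-site figures rest on equal site sizes. Ignoring site is a small addition at 68 equal sites (about 6% against a nominal 5%).

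It would be wrong to infer that the trial's main results are affected. The aim is exploratory, and no primary or secondary conclusion rests on it. It would also be wrong to infer that adjusting for arm establishes a mechanism: the number of discussions is not randomised within arm.

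**What to change.** In SAP 4.4.3 and Protocol 15.4.3, replace the correlation with:

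1. A linear mixed model of HCCQ-age on number of discussions and arm, with a random site intercept. Report the common within-arm slope with its confidence interval.
2. A second model adding the discussions-by-arm interaction, for arm-specific slopes. It must be separate, because a model with the interaction has no single common slope.

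Describe the result as a non-randomised, arm-adjusted association. In the same edit, reconcile HCCQ (SAP) with HCCQ-age (protocol) as the outcome; the models above assume HCCQ-age.

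The cost is a few sentences of SAP and protocol wording. The data, the software and the mixed-model framework are those already planned.

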#### **4.5 Missing Data**

Every effort will be made to encourage and facilitate participants' completion of questionnaires, but because of dropout, missing data will occur. We will evaluate the patterns of missing data and associations of missingness with other available variables. Under the missing at random (MAR) assumption, the parameter estimates from the mixed model analyses will be unbiased. If the data are suspected to be missing not at random (MNAR), a sensitivity analysis using pattern-mixture models will be run to determine the impact on the results.

### **5 Description of Subject Disposition in Trial Report**

Subject disposition will be described in CONSORT flow diagrams for patients, caregivers and providers (Appendix C includes data that will be used for the CONSORT flow diagram).

## **6 Reporting Conventions**

Reporting conventions will accord with the most recent edition of the AMA Manual of Style. In particular, P-values  $\geq 0.001$  will be reported to 3 decimal places; p-values less than 0.001 will be reported as “<0.001”. The mean, standard deviation, and any other statistics other than quantiles, will be reported to no more than 2 decimal places greater than the original data. Quantiles, such as median, or minimum and maximum will use the same number of decimal places as the original data. Estimated parameters, not on the same scale as raw observations (e.g. regression coefficients) will be reported to 3 significant figures.

## **7 Technical Details**

[name] with the help of statistical support staff will perform all analyses using SAS and R software. We will use SAS and R programming code as appropriate, and will follow reproducible research conventions. All programs and results will be stored on a secure network drive.

**8 Appendices**

**8.1 Appendix A: Randomization Schema**

**8.1.1 Current Sites Randomization Assignments**

*Note: Practice Site Names and NCORPs are not included in this table in order to keep study PI and statistician blinded to the randomization allocations. See sample below:*

Rand ID	Size	Randomization Allocation
1	Small	GA
3	Large	GA
3	Large	GA
3	Large	GA
3	Large	GA
3	Large	GA
3	Large	GA
3	Large	GA
3	Large	GA
4	Small	Control
5	Small	GA
6	Small	GA
9	Small	GA
10	Large	GA
10	Large	GA
10	Large	GA
10	Large	GA
10	Large	GA
11	Large	Control
11	Large	Control
11	Large	Control
11	Large	Control
11	Large	Control
11	Large	Control
11	Large	Control
11	Large	Control
11	Large	Control
11	Large	Control
11	Large	Control
11	Large	Control
11	Large	Control
11	Large	Control
11	Large	Control
11	Large	Control
11	Large	Control
11	Large	Control
11	Large	Control
11	Large	Control
11	Large	Control
11	Large	Control
11	Large	Control
11	Large	Control
11	Large	Control
11	Large	Control
11	Large	Control
11	Large	Control
11	Large	Control
11	Large	Control
11	Large	Control
11	Large	Control
11	Large	Control

### **8.1.2 Future Sites Randomization Assignments**

When new sites join the study, we first determine whether they are large or small based on their past accruals onto URCC NCORP or cancer control studies. After this determination, they are then assigned the next available practice site ID number and placed in either the “Small Site” or “Large Site” column.

